10.1. Efficacy Measures

10.1.1. Primary Efficacy Measure

The primary efficacy measure will be the proportion of patients achieving ACR20 at Week 12. ACR20 is defined as at least 20% improvement in the following ACR Core Set values:

- TJC (68 joint count)
- SJC (66 joint count)
- An improvement of $\geq 20\%$ in at least 3 of the following 5 assessments:
 1. Patient's Assessment of Pain (VAS)
 2. Patient's Global Assessment of Disease Activity (VAS)
 3. Physician's Global Assessment of Disease Activity (VAS)
 4. Patient's Assessment of Physical Function as measured by the HAQ-DI
 5. Acute phase reactant as measured by hsCRP.

10.1.2. Secondary Efficacy Measures

The secondary efficacy measures described below will be collected at the times shown in the Study Schedule ([Attachment 1](#)).

10.1.2.1. Disease Activity Score-Erythrocyte Sedimentation Rate and Disease Activity Score-High Sensitivity C-Reactive Protein

The DAS28 is a measure of disease activity in 28 joints that consists of a composite numeric score of the following variables: TJC, SJC, hsCRP *or* ESR, and Patient's Global Assessment of Disease Activity (Vander Cruyssen et al. 2005). The 28 joints to be examined and assessed as tender or not tender for TJC and as swollen or not swollen for SJC include 14 joints on each side of the patient's body: the 2 shoulders, the 2 elbows, the 2 wrists, the 10 metacarpophalangeal joints, the 2 interphalangeal joints of the thumb, the 8 proximal interphalangeal joints, and the 2 knees (Smolen et al. 1995).

10.1.2.2. ACR50 and ACR70 Indices

The ACR50 and ACR70 responses are secondary efficacy measures that are calculated as improvements of at least 50% and of at least 70%, respectively, in the ACR Core Set values identified in Section [10.1.1](#).

10.1.2.3. Hybrid American College of Rheumatology Response Measure

The hybrid ACR (bounded) response measure will be obtained as described by the ACR Committee to Reevaluate Improvement Criteria (2007); see [Table JAGS.10.1](#).

Table JAGS.10.1. Scoring Method for the Hybrid American College of Rheumatology Response Measure

ACR Status	Mean % Change in Core Set Measures ^a			
	<20	≥20, <50	≥50, <70	≥70
Not ACR20	Mean % change	19.99	19.99	19.99
ACR20 but not ACR50	20	Mean % change	49.99	49.99
ACR50 but not ACR70	50	50	Mean % change	69.99
ACR70	70	70	70	Mean % change

Abbreviations: ACR = American College of Rheumatology; ACR20 = 20% improvement in ACR criteria; ACR50 = 50% improvement in ACR criteria; ACR70 = 70% improvement in ACR criteria.

^a 1) Calculate the average percentage change in core set measures. For each core set measure, subtract score after treatment from baseline score and determine percentage improvement in each measure. Next, if a core set measure worsened by >100%, limit that percentage change to 100% (set equal to -100% bound). Then, average the percentage changes for all core set measures. 2) Determine whether the patient has achieved ACR20, ACR50, or ACR70. 3) Using the table above, obtain the hybrid ACR response measure. To use the table, take the ACR20, ACR50, or ACR70 status of the patient (left column) and the mean percentage improvement in core set items; the hybrid ACR score is where they intersect in the table.

10.1.2.4. ACR/EULAR Rheumatoid Arthritis Remission

Two ACR/EULAR definitions of RA remission will be evaluated, a “Boolean-based definition” and an “index-based definition” (Felson et al. 2011).

- Boolean-based Definition of Remission: All 4 criteria below must be met:
 - TJC28 ≤ 1
 - SJC28 ≤ 1
 - hsCRP ≤ 1 mg/dL (10 mg/L)
 - patient global DAS on VAS (0 to 10.0) ≤ 1
- Index-based Definition of Remission (see Section 10.1.2.5):
 - SDAI ≤ 3.3

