Joints will be assessed for tenderness by pressure and joint manipulation on physical examination. Any positive response on pressure, movement, or both will then be translated into a single tender-versus non-tender dichotomy. Joints will be classified as either swollen or not swollen. Swelling is defined as palpable fluctuating synovitis of the joint. Swelling secondary to osteoarthritis will be assessed as not swollen, unless there is unmistakable fluctuation.

The following joint count imputation rules will be applied.

(1). Joints that had any of the following procedures or disease conditions that occur at the screening (Visit 1) up to and including baseline (Visit 2) will be imputed as follows:

- **Arthroplasty, fusion, synovectomy, ankylosis, amputation, injury, fracture, and infection:** these will be considered “non-evaluable” from baseline up to end of the study. Joints that include “non-evaluable” joints will be prorated from baseline up to end of the study. For example, the swollen joint count score for 6 swollen plus 2 “non-evaluable” joints for DAS28 is calculated as $[6/(28-2)]*28 = 6.46$.
- **Injection:** joints that have received intra-articular and bursal injections will be collected in the data but set to painful/tender or swollen after the injection for 6 months (up to Week 24 [Visit 11]).

(2). Joints that had any of the following procedures or disease conditions that occur postbaseline (anytime during treatment with the study drugs) will be imputed as follows:

- **Amputation:** amputation that occurs postbaseline will be considered “non-evaluable” from the visit after amputation up to end of the study. Joints that include “non-evaluable” joints will be prorated from the visit after amputation up to end of the study. For example, the swollen joint count score for 6 swollen plus 2 “non-evaluable” joints for DAS28 is calculated as $[6/(28-2)]*28 = 6.46$.

- **Arthroplasty, fusion, synovectomy, and ankylosis:** if any of these procedures occur postbaseline, joints will be set to painful/tender or swollen from the visit after the procedure up to end of the study.
- **Infection, injury, and fracture:** if any of these conditions occur postbaseline, joints will be set to painful/tender or swollen from the visit after the condition until the condition is resolved.

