- **Injection:** joints that have received intra-articular and bursal injections postbaseline will be collected in the data but set to painful/tender or swollen after the injection for 6 months or end of study (whichever comes first).

The number of tender and swollen joints will be calculated by summing all joints. For patients who have an incomplete set of joints evaluated, the joint count will be adjusted to a 28- or 68-joint count for tenderness and a 28- or 66-joint count for swelling by dividing the number of affected joints by the number of evaluated joints and multiplying by 28 or 68 for tenderness and 28 or 66 for swelling.

Disease Activity Score-Erythrocyte Sedimentation Rate (DAS28-ESR) and Disease Activity Score-High Sensitivity C-Reactive Protein (DAS28-hsCRP)

The DAS28 is a measure of disease activity in 28 joints that consists of a composite numeric score of the following variables: TJC, SJC, hsCRP or ESR, and Patient's Global Assessment of Disease Activity (Vander Cruyssen et al. 2005). The 28 joints to be examined and assessed as tender or not tender for TJC and as swollen or not swollen for SJC include 14 joints on each side of the patient's body: the 2 shoulders, the 2 elbows, the 2 wrists, the 10 metacarpophalangeal joints, the 2 interphalangeal joints of the thumb, the 8 proximal interphalangeal joints, and the 2 knees (Smolen et al. 1995). The following equation will be used to calculate the DAS28- hsCRP (Vander Cruyssen et al. 2005):

$$\text{DAS28-hsCRP} = 0.56(\text{TJC28})^{1/2} + 0.28(\text{SJC28})^{1/2} + 0.36(\ln(\text{hsCRP} + 1)) + 0.014(\text{VAS}) + 0.96$$

The hsCRP value in mg/L must be used. In order to calculate DAS28-hsCRP data must be present for all 4 components: TJC28, SJC28, patient's global assessment (VAS), and hsCRP. Component-level imputation will be performed for the calculation of DAS28-hsCRP for the imputed visits summaries. If at least 1 of the 4 components is nonmissing at the visit and the patient is still enrolled in the study, then use LOCF to fill in any missing values.

Based on the DAS-hsCRP, the following will be calculated:

- $\text{DAS28-hsCRP} \leq 3.2$
- $\text{DAS28-hsCRP} < 2.6$

Similarly,

$$\text{DAS28-ESR} = 0.56(\text{TJC28})^{1/2} + 0.28(\text{SJC28})^{1/2} + 0.70 \ln(\text{ESR}) + 0.014(\text{VAS}) \text{ [If ESR} = 0 \text{ in analysis data, set } \ln(\text{ESR}) = 0\text{]}$$

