There are 3 categories, no improvement (or no response), moderate improvement (or moderate response), and good improvement (highest kind of improvement or good response). The category of no improvement also includes a worsening of RA. Hence, relative to baseline, a patient can only have a “0” change in categories, a change of “1” category or a change of “2” categories. EULAR response based on DAS28-ESR may also be evaluated.

ACR/EULAR Rheumatoid Arthritis Remission

Two new ACR/EULAR definitions of RA remission will be evaluated, a “boolean-based definition” and an “index-based definition” (Felson et al. 2011).

- Boolean-based Definition of Remission: All 4 criteria below must be met (at the same visit):
 - TJC28 ≤ 1
 - SJC28 ≤ 1
 - hsCRP ≤ 1 mg/dL (10 mg/L)
 - Patient’s Global Assessment of Disease Activity (on a 0-100 mm scale) / 10 ≤ 1
- Index-based Definition of Remission:
 - Simplified Disease Activity Index (SDAI) ≤ 3.3

Patient’s Global Assessment of Disease Activity / 10 in order to convert from a 0-100 mm scale to a 0-10 cm scale.

The hsCRP value converted to mg/dL will be used.

Functional Assessment of Clinical Illness Therapy Fatigue (FACIT-F) Scale

The FACIT-F scale (Cella and Webster 1997) is a brief, 13-item, symptom-specific questionnaire that specifically assesses the self-reported severity of fatigue and its impact upon daily activities and functioning. The FACIT-F questionnaire is presented below.

		Not at all	A little bit	Somewhat	Quite a bit	Very much
HI7	I feel fatigued.....	0	1	2	3	4
HI12	I feel weak all over.....	0	1	2	3	4
An1	I feel listless ("washed out")	0	1	2	3	4
An2	I feel tired	0	1	2	3	4
An3	I have trouble starting things because I am tired.....	0	1	2	3	4
An4	I have trouble finishing things because I am tired.....	0	1	2	3	4
An5	I have energy	0	1	2	3	4
An7	I am able to do my usual activities.....	0	1	2	3	4
An8	I need to sleep during the day.....	0	1	2	3	4
An12	I am too tired to eat.....	0	1	2	3	4
An14	I need help doing my usual activities.....	0	1	2	3	4
An15	I am frustrated by being too tired to do the things I want to do.....	0	1	2	3	4
An16	I have to limit my social activity because I am tired.....	0	1	2	3	4

The FACIT-F uses a 13-item symptom-specific questionnaire to assess the burden of self-reported fatigue caused by a chronic disease and its impact upon daily activities and function.

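### Unrounded proration of 28-joint counts turns a single affected joint into a failure of the Boolean remission criterion

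*Protocol*

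**What the plan says.** **Remission definition.** Protocol section 10.1.2.4 states "Boolean-based Definition of Remission: All 4 criteria below must be met". The joint criteria are TJC28 ≤ 1 and SJC28 ≤ 1; the others limit hsCRP and the patient global score. SAP Appendix 2 (ACR/EULAR Rheumatoid Arthritis Remission) repeats the four and requires them at one visit. It explains the unit conversion for hsCRP and the patient global score, but adds nothing on joint counts.

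**Joint counts.** SAP Appendix 2 (Joint Assessment) makes a joint non-evaluable if one of these is present between screening and baseline: "Arthroplasty, fusion, synovectomy, ankylosis, amputation, injury, fracture, and infection". Counts that include such "joints will be prorated from baseline up to end of the study". Postbaseline amputation is prorated too, from the visit after it. A general rule follows: "For patients who have an incomplete set of joints evaluated, the joint count will be adjusted to a 28- or 68-joint count for tenderness" (and likewise for swelling), "by dividing the number of affected joints by the number of evaluated joints" and multiplying by the full number. The worked example, which begins "For example, the swollen joint count score for 6 swollen plus 2" non-evaluable joints, arrives at 6.46.

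**Use of the endpoint.** Boolean remission at Weeks 12, 24 and 52 is an exploratory objective (Protocol 6.3, SAP 4.3). SAP section 6.16 compares the arms by logistic regression up to Week 24 and otherwise describes the results by visit.

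**The concern.** The Boolean limits are set on whole joints: one tender joint and one swollen joint are allowed. Proration produces fractions. Any prorated count that starts from one affected joint lands just above 1, and neither document rounds it or exempts the Boolean criteria. A programmer who follows Appendix 2 literally would apply a stricter remission definition to patients with an unevaluated joint among the 28 than to everyone else, under the same ACR/EULAR label.

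The trigger is foreseeable. Protocol inclusion criterion 3a anticipates patients with surgically treated joints, and the SAP lets an assessor record a joint as not evaluable. The general rule covers any incomplete set, so a patient with one tender joint at two visits could be in remission at one and not at the other only because one joint was not assessed.

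**Working it through.** **Inputs.** Limits TJC28 ≤ 1 and SJC28 ≤ 1 (Protocol 10.1.2.4; SAP Appendix 2). Proration (SAP Appendix 2, Joint Assessment): with *a* affected joints and *k* of the 28 not evaluated, count = *a* / (28 − *k*) × 28.

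**1. The SAP's own example.** 6 / (28 − 2) × 28 = 6.4615, which agrees with the stated 6.46. The formula is read correctly, and decimals are kept.

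**2. One affected joint (*a* = 1).**

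| *k* | Prorated count | Meets ≤ 1? |
|---|---|---|
| 0 | 28/28 = 1.000 | yes |
| 1 | 28/27 = 1.037 | no |
| 2 | 28/26 = 1.077 | no |
| 3 | 28/25 = 1.120 | no |
| 4 | 28/24 = 1.167 | no |

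**3. In general.** The count passes only if *a* ≤ (28 − *k*)/28 = 1 − *k*/28. For any *k* ≥ 1 the right side is below 1, so only *a* = 0 passes. The working limit falls from one joint to zero.

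**4. What proration itself implies.** One affected joint in 27 puts the chance that the missing joint is affected at about 1/27 = 3.7%. The chance that the full count is still 1 is then 26/27 = 96.3%. The cut-off turns a 3.7% chance into certain failure.

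**5. Who changes status.** All of the following must hold: a joint among the 28 is prorated for the measure concerned (tenderness or swelling); the raw count on that measure is exactly 1; neither raw count exceeds 1; and hsCRP and patient global both meet their limits.

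**6. Comparison with SDAI ≤ 3.3, the secondary remission endpoint.** With *k* = 1, proration adds 28/27 − 1 = 0.037 per affected joint, or 0.074 for one tender plus one swollen joint. SDAI is a sum with a limit of 3.3, so this is a slight shift. The limit itself does not change in meaning.

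**7. Illustration of size (assumptions; the documents give no such figures).** Suppose 5% to 15% of patients have a prorated joint among the 28, and 30% to 60% of those meeting the Boolean criteria have exactly one tender and/or one swollen joint, independently. The share of Boolean remissions lost is then 0.05 × 0.30 = 1.5% to 0.15 × 0.60 = 9%. If 5% to 20% of 144 patients per arm are in Boolean remission (7.2 to 28.8 patients), the loss is 7.2 × 0.015 = 0.1 to 28.8 × 0.09 = 2.6 patients per arm.

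**The case against.** The best defence is that the state of an unassessed joint is unknown. Counting only what was seen treats that joint as unaffected, which favours remission. Failing the patient is the cautious choice and matches the SAP's nonresponder handling of binary endpoints. Part of this stands: the observed-count rule does make a mildly favourable assumption. It does not justify the present rule, because proration's own logic gives only about a 3.7% chance that the missing joint is affected, and nothing in the SAP says that the Boolean limit was meant to become zero.

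It is also fair to say that the Protocol sentence and the SAP's worked example are each correct. The fault lies in combining two SAP rules.

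A reader might infer three stronger points that the documents do not support:

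- **That every patient with a replaced, fused or missed joint and one affected joint is misclassified.** A patient who fails on hsCRP, patient global or the other joint count is a non-remitter under either rule. Postbaseline arthroplasty, fusion, synovectomy, ankylosis, infection, injury, fracture and injection are not prorated; the SAP sets those joints to tender or swollen. A joint outside the 28 has no effect on these counts.
- **That a formal Week 52 comparison is affected.** SAP sections 6.11 and 6.16 limit formal comparisons to Week 24, so Week 52 is descriptive.
- **That the treatment comparison is materially biased.** The rule is the same in both arms. Under the independence assumed in the illustration the proportional loss is equal, which would at most attenuate the difference slightly.

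**Conclusion.** Wrong as written. Read literally, SAP Appendix 2 scores as not in remission any patient who otherwise meets all the Boolean criteria, has exactly one tender and/or one swollen joint, and has a joint among the 28 prorated on that measure. This follows from the text and the arithmetic alone. It assumes only that the general joint-count rules feed the Boolean criteria, and nothing in either document says otherwise.

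The consequence is probably small. The endpoint is exploratory at every visit, and no primary or secondary conclusion depends on it. The number of patients affected cannot be derived from the documents; the illustration of under three patients per arm rests wholly on assumed frequencies.

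**What to change.** Add one sentence to SAP Appendix 2, before unblinding: for Boolean remission, the limits of 1 apply to the observed number of tender and of swollen joints among the evaluable joints of the 28. Keep the unrounded prorated counts for DAS28, SDAI and CDAI, and leave unchanged the rules that set a joint to tender or swollen.

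With this change one affected joint stays at 1 and passes for every *k*. Rounding the prorated count to the nearest whole joint is a weaker alternative: it works up to nine unevaluated joints (28/19 = 1.47, rounded to 1) and fails from ten (28/18 = 1.56, rounded to 2).

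The cost is one sentence and one line of code, with no new data. The small downside is that an unassessed joint counts as unaffected for this criterion, which the SAP should say openly.

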10.1.2.5. Simplified Disease Activity Index (SDAI)

The SDAI is a tool for measurement of disease activity in RA that integrates measures of physical examination, acute phase response, patient self-assessment, and evaluator assessment. The SDAI is calculated by adding together scores from the following assessments:

- number of swollen joints (0 to 28),
- number of tender joints (0 to 28),
- CRP in mg/dL (0.1 to 10.0),
- patient global DAS on VAS (0 to 10.0), and
- evaluator global health score on VAS (0 to 10.0) (Aletaha and Smolen 2005)

Disease remission according to ACR/EULAR index-based definition of remission is defined as an SDAI score of ≤3.3 (Felson et al. 2011).

10.1.2.6. Clinical Disease Activity Index (CDAI)

The CDAI is similar to the SDAI, but it allows for immediate scoring because it does not use a laboratory result. The CDAI is calculated by adding together scores from the following assessments:

- number of swollen joints (0 to 28),
- number of tender joints (0 to 28),
- patient global DAS on VAS (0 to 10.0), and
- evaluator global health score on VAS (0 to 10.0) (Aletaha and Smolen 2005)

Remission is defined as a CDAI score of ≤ 2.8 (Felson et al. 2011).

10.1.2.7. European League Against Rheumatism Responder Index

Assessments of patients with RA by EULAR response criteria will be used to categorize patients as nonresponders, moderate responders, good responders, or responders (moderate + good responders) according to [Table JAGS.10.2](#) (van Gestel et al. 1998).

Table JAGS.10.2. Categorization of Patients as Nonresponders, Moderate Responders, or Good Responders

Postbaseline Level of DAS28	Improvement Since Baseline in DAS28		
	>1.2	≤ 1.2 and > 0.6	≤ 0.6
DAS28 ≤ 3.2	Good response	Moderate response	No response
$3.2 < \text{DAS28} \leq 5.1$			
DAS28 > 5.1			

Abbreviation: DAS28 = Disease Activity Score modified to include the 28 diarthrodial joint count.

10.1.2.8. Van der Heijde Modified Total Sharp Score (mTSS)

Structural progression will be measured using the mTSS (van der Heijde 2000). During screening, all patients meeting entry criteria will have a single posteroanterior radiographic assessment of the left and right hand/wrist and a single dorsoplantar radiographic image taken of the left and right foot. Alternatively, images taken within 4 weeks prior to baseline may be used. Images taken at screening (or within 4 weeks of screening) will be reviewed centrally by qualified readers for evidence of erosive bony change(s). These initial radiographs will serve as the baseline radiographs for comparison throughout the study. If a patient undergoes rescreening, radiographic images acquired as part of initial screening and within 10 weeks of randomization may be used. Radiographs (that is, a single posteroanterior view of each hand and a single dorsolantar view of each foot) will be obtained at Weeks 16, 24, and 52.

For patients who discontinue prematurely from the study, x-rays will be performed at the early termination visit only if the previous x-rays were taken more than 12 weeks earlier.

The mTSS (van der Heijde 2000) quantifies the extent of bone erosions and joint space narrowing for 44 and 42 joints, respectively, of the hands/wrists and feet with higher scores

representing greater damage. X-rays will also be assessed for joint space narrowing and bone erosions.

Quality control will be performed for proper imaging examination technique prior to allocation of the images to the central readers. The independent read of x-ray images will be performed by 2 primary readers and 1 adjudicator, when necessary, based on predefined criteria. The 2 primary readers will each read 100% of the study patients. All time points will be displayed in random order for a given patient. The reader will have no knowledge of the true chronologic order, patient identity, or treatment group. To ensure a consistent read by the independent readers, an inter-/intra-reader variability assessment will be included in the central imaging core laboratory independent read. Repeat x-rays will be requested for all images obtained that are of poor quality as defined in the Image Acquisition Guidelines.

10.2. Health Outcome Measures

The health outcome measures listed below will be administered. Country-specific translations of each measure will be available in this study. Items being measured using a paper diary should be completed at the end of the patient's day (typically their bedtime).

- Morning Joint Stiffness Severity Numeric Rating Scale (NRS): The Morning Joint Stiffness NRS is a patient-administered, single-item, 11-point horizontal scale anchored at 0 and 10, with 0 representing “no joint stiffness” and 10 representing “joint stiffness as bad as you can imagine.” Patients rate their morning joint stiffness each day (using a paper diary) by selecting the one number that describes their overall level of joint stiffness at the time they woke up.
- Duration of morning joint stiffness:
 - Patient diary: The duration of morning joint stiffness is a patient-administered item that allows for the patients to enter the length of time in hours and minutes that their morning joint stiffness lasted each day.
 - Electronic PRO (tablet): The duration of morning joint stiffness is a patient-administered item that allows for the patients to enter the length of time in minutes (using 15-minute increments) that their morning joint stiffness lasted on the day prior to that visit (using an electronic patient-reported outcomes [ePRO] tablet).
- Recurrence of joint stiffness: The recurrence of joint stiffness throughout the day is a patient-administered single-item question assessed each day (using a paper diary) that asks “Did you have any joint stiffness throughout today, other than when you woke up?” (Yes/No)
- Tiredness Severity Numeric Rating Scale (Worst Tiredness NRS):
 - Patient diary: The Worst Tiredness NRS is a patient-administered, single-item, 11-point horizontal scale anchored at 0 and 10, with 0 representing “no tiredness” and 10 representing “as bad as you can imagine.” Patients rate their tiredness each day (using a paper diary) by selecting the one number that describes their worst level of tiredness.

- Electronic PRO (tablet): The Worst Tiredness NRS is a patient-administered, single-item, 11-point horizontal scale anchored at 0 and 10, with 0 representing “no tiredness” and 10 representing “as bad as you can imagine.” Patients rate their tiredness by selecting the one number that describes their worst level of tiredness during the past 24 hours.
- Severity of joint pain Numeric Rating Scale (Worst Joint Pain NRS):
 - Patient diary: The Worst Joint Pain NRS is a patient-administered, single-item, 11-point horizontal scale anchored at 0 and 10, with 0 representing “no pain” and 10 representing “pain as bad as you can imagine.” Patients rate their joint pain each day (using a paper diary) by selecting the one number that describes their worst level of joint pain.
 - Electronic PRO (tablet): The Worst Joint Pain NRS is a patient-administered, single-item, 11-point horizontal scale anchored at 0 and 10, with 0 representing “no pain” and 10 representing “joint pain as bad as you can imagine.” Patients rate their joint pain by selecting the one number that describes their worst level of joint pain during the past 24 hours.
- HAQ-DI: The HAQ-DI is a patient-reported questionnaire that is commonly used in RA to measure disease-associated disability (assessment of physical function). It consists of 24 questions referring to 8 domains: dressing/grooming, arising, eating, walking, hygiene, reach, grip, and activities (Fries et al. 1980, 1982; Ramey et al. 1996). The disability section of the questionnaire scores the patient’s self-perception on the degree of difficulty (0 = without any difficulty, 1 = with some difficulty, 2 = with much difficulty, and 3 = unable to do) when dressing and grooming, arising, eating, walking, hygiene, reach, grip, and performing other daily activities. The reported use of special aids or devices and/or the need for assistance of another person to perform these activities is also assessed. The scores for each of the functional domains will be averaged to calculate the functional disability index.
- FACIT-F scale: The FACIT-F scale (Cella and Webster 1997) is a brief, 13-item, symptom-specific questionnaire that specifically assesses the self-reported severity of fatigue and its impact upon daily activities and functioning. The FACIT-F uses 0 (“not at all”) to 4 (“very much”) numeric rating scales to assess fatigue and its impact in the past 7 days. Scores range from 0 to 52 with higher scores indicating less fatigue.
- WPAI-RA: The WPAI-RA questionnaire was developed to measure the effect of general health and symptom severity on work productivity and regular activities. It contains 6 items covering overall work productivity (health), overall work productivity (symptom), impairment of regular activities (health), and impairment of regular activities (symptom). Scores are calculated as impairment percentages (Reilly et al. 1993).
- EQ-5D-5L: The EQ-5D-5L is a standardized measure of health status that provides a simple, generic measure of health for clinical and economic appraisal. The EQ-5D-5L consists of 2 components: a descriptive system of the respondent’s health and a rating of his or her current health state using a 0- to 100-mm VAS. The descriptive system comprises the following 5 dimensions: mobility, self-care, usual activities, pain/discomfort, and anxiety/depression. Each dimension has 5 levels: no problems,

slight problems, moderate problems, severe problems, and extreme problems. The respondent is asked to indicate his/her health state by ticking (or placing a cross) in the box associated with the most appropriate statement in each of the 5 dimensions. It should be noted that the numerals 1 to 5 have no arithmetic properties and should not be used as a cardinal score. The VAS records the respondent's self-rated health on a vertical VAS in which the endpoints are labeled "best imaginable health state" and "worst imaginable health state." This information can be used as a quantitative measure of health outcome. The EQ-5D-5L health states, defined by the EQ-5D-5L descriptive system, may be converted into a single summary index by applying a formula that essentially attaches a value (also called weights) to each of the levels in each dimension (Brooks 1996; EuroQol Group 2011 [WWW]; Herdman et al. 2011).

- **Quick Inventory of Depressive Symptomatology Self-Rated-16 (QIDS-SR₁₆):** The QIDS-SR₁₆ is a 16-item, self-report instrument intended to assess the existence and severity of symptoms of depression as listed in the American Psychiatric Association's *Diagnostic and Statistical Manual of Mental Disorders*, 4th Edition (APA 1994). Patients are asked to consider each statement as it relates to the way they have felt for the past 7 days. There is a 4-point scale for each item ranging from 0 to 3. The 16 items corresponding to 9 depression domains are summed to give a single score ranging from 0 to 27. Additional information and the QIDS-SR₁₆ questions may be found on the University of Pittsburgh Epidemiology Data Center web site (Inventory of Depressive Symptomatology/Quick Inventory of Depressive Symptomatology [WWW]) (Rush et al. 2003; Trivedi et al. 2004).
- **Healthcare resource utilization:** The healthcare resource utilization data will be collected by site staff regarding the number of visits to medical care providers such as general practitioners, specialists, physical or occupational therapists, and other non-physical care providers for services outside of the clinical study; emergency room admissions; hospital admissions; and concomitant medications related to the treatment of RA. These data will be collected to support economic evaluations of treatment.

